9.2 Definition of Measurable Disease

Measurable disease

Measurable disease is defined by the presence of at least one measurable lesion as defined below and adapted from the RECIST 1.1 criteria (Eur J Cancer. 2009 Jan;45(2):228-47). All measurements must be recorded in metric notation. If measurable disease is restricted to a solitary lesion, its malignant nature should previously have been confirmed by cytology/histology.

Since some melanoma metastases contain melanin pigment and since successfully treated liver metastases tend to retain infused ethiodized oil, evaluation of radiological response after embolization treatments is generally difficult. Therefore, we will obtain both CT scan and MRI of the liver for the precise evaluation of radiological responses. However, the same modality will be used for measurement of the liver metastases and assessment of the response.

The longest diameter (LD) of the largest liver lesion should be \geq 10 mm by CT scan or MRI in order to become eligible for the study.

Non-measurable disease

All other lesions including small lesions (<10 mm on CT scans) are considered "non-measurable". The following lesions are also considered as "non-measurable": Bone lesions, leptomeningeal disease, ascites, pleural/pericardial effusion, abdominal masses that are not confirmed and followed by imaging techniques, tumors treated by irradiation or by intra-tumor injection therapy.

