4.0 SUBJECT SELECTION AND WITHDRAWAL

4.1 Inclusion Criteria

- Histologically confirmed metastatic uveal melanoma in the liver. Patients must have at least one measurable liver metastasis that is ≥ 10 mm in longest diameter by CT scan or MRI.
- 2. The total volume of the tumors must be less than 50% of the liver volume.
- 3. Willingness and ability to give informed consent.
- 4. Agreement to access archival tissue or agreement for tumor biopsy prior to treatment
- 5. ECOG performance status of 0, or 1
- 6. Adequate renal and bone marrow functions: serum creatinine ≤ 2.0 mg/dl, granulocyte count ≥ 1000/mm3, and platelet count ≥ 100,000/mm3.
- 7. Adequate liver function: bilirubin ≤ 2.0 mg/ml, albumin ≥ 3.0 g/dl, PT/PTT less than 1.5 times normal, AST and ALT less than 3x ULN and alkaline phosphatase less than 1.5 times ULN (grade 1).
- 8. Age \geq 18 years of age.
- 9. Women must not be pregnant or breast-feeding. See section 4.2.1
- 10. Women of child-bearing potential must use at least two other accepted and effective methods of contraception and/or to abstain from sexual intercourse for at least 23 weeks after the last dose of nivolumab and/or ipilimumab and sexually active males must use at least two other accepted and effective methods of contraception and/or to abstain from sexual intercourse for at least 31 weeks after the last dose of nivolumab and/or ipilimumab. See section 4.2.1

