4.2 Exclusion Criteria

- 1. Failure to meet any of the criteria set forth in the Inclusion criteria section
- 2. Previous systemic exposure to anti-CTLA-4 antibody or anti-PD1 antibody
- 3. Previous liver-directed treatments including chemoembolization, radiosphere, hepatic arterial perfusion, or drug-eluting beads; liver resection and focal ablation are permitted.
- 4. Presence of symptomatic liver failure including ascites and hepatic encephalopathy.
- 5. Presence of untreated brain metastases. If patients have had previous treatment for the brain metastasis, an MRI or CT scan of the brain must confirm the stabilization of the brain metastasis for more than 2 months.
- 6. Presence of uncontrolled hypertension or congestive heart failure, or acute myocardial infarction within 6 months of entry.
- 7. Presence of any other medical complication that implies survival of less than six months
- 8. Uncontrolled severe bleeding tendency or active GI bleeding.
- 9. Significant allergic reaction to contrast dye or GM-CSF.
- 10. Immunosuppressive treatments within 4 weeks prior to embolization, unless prednisone ≤ 5mg or equivalent
- 11. Pregnancy or breast-feeding women.
- 12. Patients with active hepatitis with SGOT and SGPT equal or greater than 5 times normal
- 13. Biliary obstruction, biliary stent or prior biliary surgery except cholecystectomy
- 14. Positive for known HIV Infection

- 15. Uncontrolled Chronic Obstructive Pulmonary Disease or previous known pulmonary fibrosis
- 16. Active infection.
- 17. Auto-immune disease including inflammatory bowel disease, lupus, rheumatoid arthritis, but not including hypothyroidism or psoriasis if condition has been stable for 2 months or greater.

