5.6 Prior and Concomitant Therapy

For immune-related adverse events, steroid treatment will be allowed if it is tapered to 5 mg of prednisone or less before initiation of next cycle. Patients cannot have had prior exposure to anti-CTLA4 or anti-PD1 therapy. They cannot have had prior regional liver directed therapy but may have had liver resection or focal ablation. Palliative radiation is allowed during treatment. Patients who had cellular immunotherapy must have a washout period of at least 90 days prior to first treatment cycle. Patients who had other systemic therapies or radiation treatment must have a least a two week washout period prior to first treatment cycle. Bone strengthening agents such as zolendronic acid or denosumab are also allowed for bone metastases.

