7.2.1 Analysis Population

The evaluable population includes all subjects enrolled who receive at least four combination treatments (IPI + NIVO + IEMBO at initial every 3 week intervals or NIVO + IEMBO if IPI dropped due to toxicity and IEMBO alone if NIVO dropped due to toxicity) and complete assessment after four treatments.

The As-treated population includes all subjects who receive any treatment and will be used to evaluate baseline characteristics as well as all secondary endpoints for safety and efficacy as the collected data allows.

7.2.2 Primary Endpoint:

The primary endpoint is the best hepatic response (CR + PR + SD) by response criteria (RECIST 1.1) after four combination treatments. The estimate of the hepatic metastasis stabilization rate will be presented with corresponding 95% confidence intervals. The method of Atkinson and Brown will be used to adjust for the two-stage design.

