9.3 Baseline Documentation of "Target" and "Non-Target" Lesions

Target Lesions (Indicator Lesions)

The target lesions are defined as measurable lesions that will be used for evaluation of response. For this protocol, target lesions require serial measurement of a longest diameter (LD) and should be ≥10 mm by CT scan or MRI at the time of study entry.

Target lesions (up to a maximum number of 6 for the liver metastases) must be identified and measured at baseline prior to the initiation of embolization. Target lesions must be selected on the basis of their size (LD) and suitability for repetitive measurements.

Non-Target Lesions

All other lesions (or sites of melanoma) must be identified as "non-target" and their location and characteristics must be recorded at baseline. During follow-up evaluations, these lesions must be followed as "present" or "absent".

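### Prior focal ablation is allowed, but section 9.2 does not class ablated liver lesions as non-measurable, so they can be target lesions and bias the stabilization rate upward

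*Combined protocol and SAP*

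**What the plan says.** Eligibility. Exclusion criterion 3 (section 4.2) bars earlier liver-directed treatments but adds that "liver resection and focal ablation are permitted". Section 5.6 repeats this: "They cannot have had prior regional liver directed therapy but may have had liver resection or focal ablation". Neither sets a condition on the ablated lesion, such as regrowth, viability or time since ablation. Inclusion criterion 1 (section 4.1) reads: "Patients must have at least one measurable liver metastasis that is ≥ 10 mm in longest diameter by CT scan or MRI".

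Measurability and targets. Section 9.2 makes measurability a matter of size and then lists exceptions. The only exceptions based on earlier local treatment are "tumors treated by irradiation or by intra-tumor injection therapy". Section 9.3 states: "Target lesions must be selected on the basis of their size (LD) and suitability for repetitive measurements". Up to six liver targets are allowed.

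Endpoint. Section 7.2.2 states: "The primary endpoint is the best hepatic response (CR + PR + SD) by response criteria (RECIST 1.1) after four combination treatments". Under section 9.5, stable disease (SD) is whatever is neither response nor progression, and progression (PD) needs a rise of at least 20% in the summed longest diameters, unequivocal non-target progression, or a new lesion of 10 mm or more in a treated lobe.

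Related safeguards. Section 9.2 adds: "If measurable disease is restricted to a solitary lesion, its malignant nature should previously have been confirmed by cytology/histology". Inclusion criterion 4 asks for "Agreement to access archival tissue or agreement for tumor biopsy prior to treatment".

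**The concern.** Section 9.2 already accepts that a tumor treated locally before entry is a poor gauge of what the study treatment does, because it excludes irradiated and injected tumors. Focal ablation is the one non-surgical local liver treatment that eligibility expressly permits, and it is missing from that list. An ablation zone may contain little viable tumor and may stay the same size whatever the study treatment does. This is an inference about ablated tissue, but it is the same reasoning the protocol applies to the two treatments it names.

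An unchanged target contributes to SD, and SD is a success. Inert tissue in the summed diameter also hides growth elsewhere. Its effect on the primary endpoint runs one way. It can turn a PD into an SD, which changes the result. It can also turn a partial response into an SD, but both are successes. The trial has no control arm to absorb such a bias, and the rate is tested against a fixed 60%.

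**Working it through.** **1. The stated design.** Inputs, from the Study Summary and sections 7.1 and 7.2: 13 patients in stage 1, stop at 8 or fewer successes; 35 in total, reject the null at 26 or more; null rate 60%, alternative 80%.

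- Early stop: P(X1 ≤ 8), with X1 ~ Bin(13, p).
- Rejection: sum over x = 9 to 13 of P(X1 = x) × P(X2 ≥ 26 − x), with X2 ~ Bin(22, p).
- At p = 0.60: early stop 0.647, rejection 0.0499.
- At p = 0.80: rejection 0.808, so the type II error is 0.192.

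After rounding these agree with the plan's 0.65, 5%, 80% and 19%. The type I error has almost no slack below 0.05.

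**2. Dilution of the summed diameter.** Let w be the share of the baseline sum that is inert and unchanging. PD requires a 20% rise in the whole sum, so the viable targets must grow by 0.20 / (1 − w).

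| Inert share w | Viable growth needed for PD |
|---|---|
| 0 | 20% |
| 25% | 0.20 / 0.75 = 27% |
| 50% | 0.20 / 0.50 = 40% |
| 67% | 0.20 / 0.333 = 60% |

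Two examples with assumed sizes show the spread:

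- A 40 mm zone plus one 20 mm viable lesion: sum 60 mm, PD at +12 mm, and 12/20 = 60% growth.
- The same zone plus five 20 mm viable lesions: sum 140 mm, PD at +28 mm, and 28/100 = 28% growth.

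The first is a high-dilution case. With six targets the effect can be modest.

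**3. Patients with only ablated targets.** Assume a share f of patients has only inert targets and always scores SD, and the true rate in the rest is 60%. The effective rate is 0.60(1 − f) + f = 0.60 + 0.40f.

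| f (assumed) | Effective rate | False-positive risk | Early stop |
|---|---|---|---|
| 0% | 0.600 | 0.0499 | 0.647 |
| 3% | 0.612 | 0.066 | 0.613 |
| 5% | 0.620 | 0.079 | 0.590 |
| 10% | 0.640 | 0.120 | 0.530 |

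With exactly one or two such patients among the 35, the risk is 0.064 or 0.081.

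These are upper bounds, because SD is not certain for such patients. If they scored as successes 90% of the time, the effective rate at f = 5% would be 0.57 + 0.045 = 0.615 and the risk 0.071. At f = 10% it would be 0.54 + 0.09 = 0.630 and 0.098. The documents give no value for f.

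**The case against.** A reader might infer that an inert ablation zone can by itself bring a patient into the trial and then automatically count as a success, so that the true type I error is 8% to 12%. The documents do not support that.

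- SD is not automatic. Under section 9.4, non-target progression or a new lesion of 10 mm or more in a treated lobe gives PD, and SD without confirmation after at least four weeks is recategorized as PD.
- Inclusion criterion 1 requires a metastasis and histologically confirmed liver disease. A solitary measurable lesion needs earlier cytology or histology. Section 6.1.1 lists a core biopsy before treatment.
- Section 9.3 also requires suitability for repeated measurement, which lets an investigator pass over an ablation margin.
- No ablation frequency is given, and patients with only ablated targets are probably uncommon.
- Section 9.2 is adapted from RECIST 1.1, which may deal with locally treated lesions. The series behind the 60% may have included ablated patients, in which case part of the bias is shared. Neither can be checked here.

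Most of this stands as a limit on size, but it does not close the gap. The solitary-lesion rule is met by tissue taken before the ablation, and inclusion criterion 4 and section 10.2 accept archival tissue. Non-targets are recorded only as present or absent (section 9.3), and new lesions in an untreated lobe do not count as liver progression (section 9.4). An unchanging lesion that is rescanned passes the four-week confirmation. The protocol writes out its own list of non-measurable lesions, and ablated lesions are not on it.

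**Conclusion.** The gap is real. As written, a previously ablated liver lesion of 10 mm or more can be measurable and can be a target, and this can bias the stabilization rate upward against the 60% null. The likelier route is dilution: viable targets must grow 27% to 60% rather than 20% when inert tissue is 25% to 67% of the baseline sum, assuming that tissue does not change size. The rarer route, patients with only ablated targets, would raise the false-positive risk from 0.0499 to at most 0.066, 0.079 or 0.120 at assumed shares of 3%, 5% or 10%. Those are upper-bound scenarios, not estimates for this trial. The point calls for a cheap improvement to one definition. It does not put the design, sample size or cut-offs in question.

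**What to change.** In section 9.2, add to the non-measurable list: *lesions treated by focal ablation, unless growth of the lesion since ablation is documented on imaging*. Inclusion criterion 1 and section 9.3 both rest on the word *measurable*, so they follow without further edits. Leave the rule for irradiated and injected lesions as it is; a growth exception written into inclusion criterion 1 for those lesions would conflict with section 9.2.

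For patients already enrolled, flag every target lesion that was ablated before entry and report the primary endpoint with and without those lesions as a sensitivity analysis.

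Cost: one line in an amendment and one extra table. Earlier post-ablation imaging must be consulted where it exists, and the rare patient whose only measurable lesion is non-growing ablated tissue becomes ineligible. Sample size, cut-offs and on-study scans do not change.

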9.3 Baseline Documentation of "Target" and "Non-Target" Lesions

Target Lesions (Indicator Lesions)

The target lesions are defined as measurable lesions that will be used for evaluation of response. For this protocol, target lesions require serial measurement of a longest diameter (LD) and should be ≥10 mm by CT scan or MRI at the time of study entry.

Target lesions (up to a maximum number of 6 for the liver metastases) must be identified and measured at baseline prior to the initiation of embolization. Target lesions must be selected on the basis of their size (LD) and suitability for repetitive measurements.

Non-Target Lesions

All other lesions (or sites of melanoma) must be identified as "non-target" and their location and characteristics must be recorded at baseline. During follow-up evaluations, these lesions must be followed as "present" or "absent".

9.4 Evaluation of overall response in the liver metastases

Clinical response in the liver metastases will be evaluated using CT scans or MRI of the abdomen initially following four combination treatments and then after every two IEMBO treatments. The same modality must be used for serial measurements of target lesions. The sum of the longest diameter (LD) of up to 6 target liver lesions will be used to determine response. The investigators must identify target indicator lesions and measure them prior to the first embolization as baseline. The investigators will then measure the same target lesions after every two IEMBO treatments.

The sum of the baseline LDs will be compared to the sum of LDs after every two IEMBO treatments following the scans after the first four treatments. New lesions will be defined as lesions that appear in the treated lobe(s) of the liver after the last evaluation and should be \geq 10 mm in longest diameter. Development of new lesion(s) in an untreated lobe (area) of the liver **will not** be considered as "Progressive Disease" for evaluation of liver response. These lesions will be treated in the subsequent embolization procedures and

they will be included in the evaluation for response after completion of two additional embolizations.

Target Liver Lesions	Non-Target Liver Lesions	New Liver Lesions in the treated lobes	Overall Liver Response
CR	CR	No	CR
CR	SD	No	PR
PR	Non-PD	No	PR
SD	Non-PD	No	SD
PD	Any	Yes or No	PD
Any	PD	Yes or No	PD
Any	Any	Yes	PD

To be assigned a status of CR or PR, changes in tumor measurements must be confirmed by the follow-up assessment using the same imaging test at a minimum interval of 4 weeks. The patients who have a CR or PR without confirmatory assessment will be categorized as SD. In the case of SD, follow-up measurements must have met the SD criteria at least once at a minimum interval of 4 weeks. The patients who have a SD without confirmatory assessment will be categorized as PD.

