9.5 Response criteria for liver metastases

The response of liver metastases will be evaluated by MRI or CT scans using the criteria

Complete Response (CR)	Disappearance of all target and non-target liver lesions
Partial Response (PR)	> 30% decrease in the sum of the longest diameters ("sum LD") relative to baseline sum LD with at least stable non-target liver lesions
Stable Disease (SD)	Absence of change which would qualify as response or progression
Progression (PD)	≥ 20% increase in the sum LD in target liver lesions or unequivocal progression of non-target liver lesions in the treated lobe(s) Appearance of one or more new liver lesions ≥10 mm in the treated lobe(s)

adapted from the international criteria proposed by RECIST 1.1. However, since there can be post embolization changes in liver tumors that can sometimes be read as lesion enlargement, post treatment changes will be considered when lesions are measured.

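### The reference sum for the 20% progression threshold is unstated in 9.5 and only baseline is named in 9.4, so target-lesion progression after shrinkage can be scored late and hepatic PFS lengthened

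*Combined protocol and SAP*

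**What the plan says.** Section 9.4 has up to six target liver lesions measured before the first embolization and again after every two embolizations. On the comparison it says "The sum of the baseline LDs will be compared to the sum of LDs after every two IEMBO treatments", and the sentence goes on to limit itself to scans that come after the assessment at four treatments.

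Section 9.5 gives the response criteria, described as "adapted from the international criteria proposed by RECIST 1.1". The partial-response row names its reference: the decrease is "relative to baseline sum LD with at least stable non-target liver lesions". The progression row requires a "≥ 20% increase in the sum LD in target liver lesions" and names no reference. The same section gives two routes to progression that do not depend on the sum: unequivocal non-target progression, and a new lesion of at least 10 mm in a treated lobe.

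Section 9.6 runs PFS from the start of treatment to progression confirmed by imaging or physical examination, with hepatic and extra-hepatic intervals also measured separately. Section 7.2.2 states: "The primary endpoint is the best hepatic response (CR + PR + SD) by response criteria (RECIST 1.1) after four combination treatments".

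**The concern.** A threshold expressed as a percentage increase has no meaning until its reference sum is fixed. Someone scoring scans from sections 9.4 and 9.5 finds one reference in the text, the baseline sum. With that reference, a patient whose liver tumors shrink and then regrow has to cover all the lost ground and a further 20% before the target lesions count as progressing.

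The delay falls only on patients who shrank, and it grows with the depth of shrinkage. Hepatic PFS, a secondary endpoint, would be longer than it would be if regrowth were measured from its lowest point. Two readers could also score the same measurements differently.

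**Working it through.** The documents give no figure for this point, so there is none of the plan's to reproduce. The two-stage design (13 then 35 patients; stop at 8 or fewer; success at 26 or more) does not depend on it. That design recomputes to a type I error of 0.0499, power of 0.808 and early stopping at a 60% rate of 0.647, in line with section 7.2 after rounding.

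**Inputs.** Progression threshold: 20% (9.5). Reference named for maintenance scans: baseline (9.4). Alternative reference: the smallest sum recorded, baseline included. Baseline sum set to 100. Let *s* be the fractional fall to the smallest sum.

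**Step 1, threshold.** Baseline reference: 1.2 × 100 = 120 for every patient. Smallest-sum reference: 1.2 × 100(1 − s). Regrowth from the smallest sum needed under the baseline reference: 1.2/(1 − s) − 1.

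| Fall | Smallest sum | Progression, smallest-sum reference | Progression, baseline reference | Regrowth needed, baseline reference |
|---|---|---|---|---|
| 10% | 90 | 108 | 120 | 33% |
| 20% | 80 | 96 | 120 | 50% |
| 30% | 70 | 84 | 120 | 71% |
| 40% | 60 | 72 | 120 | 100% |
| 50% | 50 | 60 | 120 | 140% |

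For example, 1.2/0.7 − 1 = 0.714 and 1.2/0.5 − 1 = 1.40. Under the smallest-sum reference the last column would read 20% throughout.

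**Step 2, time (illustration only).** Assume steady regrowth of *g* per 4 weeks and no other route to progression. The extra time is 4 × [ln(1.2/(1 − s)) − ln(1.2)]/ln(1 + g) = 4 × ln(1/(1 − s))/ln(1 + g) weeks.

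- 30% fall, g = 5%: 4 × 0.3567/0.0488 = about 29 weeks.
- 30% fall, g = 10%: 4 × 0.3567/0.0953 = about 15 weeks.
- 30% fall, g = 20%: 4 × 0.3567/0.1823 = about 8 weeks.
- 50% fall, g = 10%: 4 × 0.6931/0.0953 = about 29 weeks.

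Maintenance scans follow every two 28-day cycles, about 8 weeks apart, so actual delays would come in steps of that length. The 8-to-29-week range corresponds to roughly one to four scans.

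**Step 3, primary endpoint.** Best response is counted from week 12 (3.2), and for unconfirmed responses 9.4 says "The patients who have a CR or PR without confirmatory assessment will be categorized as SD", so on a plain reading later regrowth does not undo those successes. Two routes remain:

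- *Confirmation of stable disease.* Section 9.4 requires stable disease to be met again at least 4 weeks later and otherwise counts it as progression. Take a sum of 80 at week 12. A follow-up sum from 96 to just under 120 confirms stable disease under the baseline reference and is progression under the smallest-sum reference.
- *Shrinkage at the scan between cycles 2 and 3, regrown by week 12.* This matters only if a sum is recorded at that scan. The schedule in 15.1 lists tumor measurement before treatment, after four cycles, at follow-up visits and at exit, and has no column for that scan. The wording in 9.4 about measuring after every two embolizations could include it. If no sum is recorded there, baseline is the only earlier sum at week 12 and the two references agree.

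**The case against.** The strongest reply is that the plan nowhere writes that progression means 20% above baseline. Baseline is attached to partial response only, the progression row is silent, and RECIST 1.1 is cited in 3.2, 6.1.4, 7.2.2, 9.2 and 9.5, so a reader could take the missing reference from there. The 9.4 sentence covers maintenance scans, not the cycle 2–3 or week-12 scan. Section 6.1.5 also uses a different reference, a further rise of more than 10% from the scan that first suggested progression.

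Part of this stands. What can be proved is an undefined reference, with baseline the only one written for maintenance scans. The citation does not safely close the gap. Section 9 calls its rules an adaptation and writes out its own, including the discounting of new lesions in an untreated lobe, and it does not reproduce the cited standard's reference for progression. The 6.1.5 rule operates only once progression is already suspected, so it cannot define the first call.

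A reader might also infer that no patient who shrank can be called progressing until 120% of baseline. The documents do not support that: new lesions of at least 10 mm in treated lobes, non-target progression and physical examination all count regardless of the sum. These routes protect only in part, because new lesions in untreated lobes are excluded and 9.3 follows non-target lesions only as present or absent.

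Finally, hepatic PFS is secondary, single-arm and described by Kaplan-Meier estimates (7.2.3), with no test or decision rule attached.

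**Conclusion.** The point holds for target-lesion progression and hepatic PFS. The regrowth requirements of 71% and 140% after falls of 30% and 50% are exact arithmetic, given baseline as the reference. The direction of any effect on hepatic PFS is upward. Its size cannot be computed, because the documents do not give the share of patients who shrink and then regrow in target lesions alone. The delays in weeks rest on assumed growth rates and are illustrations, not estimates of bias.

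A reader might infer that the primary stabilization rate, and with it the type I error, is materially inflated. The documents do not support that. The effect is confined to the two narrow routes in the working and may be nil. If the 60% rate for embolization alone was scored against baseline too, the comparison with the null would be affected even less; the documents do not say how it was scored. Since the final rule turns on one count, 26 of 35, it is still worth removing the ambiguity.

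This should be corrected; confidence is moderate, because the baseline reading is the only one written but is not stated in the progression row itself.

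**What to change.** In 9.4 and 9.5, state that for scoring hepatic response and hepatic PFS the 20% increase is measured from the smallest sum of longest diameters recorded on study, baseline included. Keep baseline as the reference for partial response, and reconcile both sections with the RECIST 1.1 citation. Say also whether a sum is recorded at the scan between cycles 2 and 3, and align 15.1 with that.

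The cost is about one sentence in each section. No further scans are needed for the maintenance comparison, and the sample size and cut-offs do not change. Existing measurements can be rescored. The downside is that reported hepatic PFS may be shorter.

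Progression also governs continuation of treatment and removal from the study (4.3.1 and 6.1.4 to 6.1.6). Those passages must be reconciled with the chosen endpoint definition. This point concerns endpoint scoring only and does not propose a stopping rule.
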